5.6 Study Completion and Discontinuation

5.6.1 Study completion and post-study treatment

A patient will be considered to have completed the study when the patient has completed the last visit planned in the protocol.

Study completion for a patient can occur after he/she has completed 52 weeks of treatment in Treatment Period 1, or after the additional 104 weeks of treatment in optional Treatment Period 2 (total of 156 weeks of treatment) or if they have prematurely withdrawn. Completion of the study will be when all randomized patients have met the definition of study completion described above and have completed the post-treatment follow-up visit.

Patients who have been screened when the enrollment target has been met will be allowed to proceed onto study participation.

Patients completing the study after Treatment Period 1 or Treatment Period 2 will not be given further access to study drug because the risk/benefit ratio will not yet have been substantiated and there are already other marketed therapeutic alternatives available to treat these patients. At the time of study completion or early termination, all patients will be placed on the appropriate asthma treatment as prescribed by the investigator.

For all patients/subjects a safety follow-up visit (visit 401) should be conducted (e.g. by telephone for males and females of non-child bearing potential; women of childbearing potential must come in to the clinic for pregnancy testing at Visit 401) 30 days after last visit (299, Week 52 for patients not continuing into Treatment Period 2 and visit 399, week 156 for patients completing Treatment Period 2). The information to be collected at this follow up visit includes concomitant medications, adverse events, pregnancy testing and survival status.

The investigator must provide appropriate advice on the continued use of basic contraception for at least one week (at least 5 half-lives of QAW039) after study completion (Visit 299 or Visit 399, as appropriate) or premature study drug discontinuation and follow up with the subject as appropriate at least to the end of this period.

The investigator must provide follow-up medical care for all patients who are prematurely withdrawn from the study, or must refer them for appropriate ongoing care.

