If discontinuation of study treatment occurs, the patient should NOT be considered withdrawn from the study. The patient should return to the clinic as soon as possible, after discontinuation of study drug, for a study treatment discontinuation visit. Treatment discontinuation visit assessments detailed in the “unscheduled treatment discontinuation visit” (TD) in [Table 6-1](#) should be completed and recorded in the eCRF. The investigator must determine the primary reason for the patient’s premature discontinuation of study treatment and record this information on the Dosage Administration eCRF.

Patients who discontinue study treatment will be asked to remain in the study and complete all study visits. Patients withdrawn from study treatment will receive SoC asthma therapy according to investigator judgment.

If the patient cannot or is unwilling to attend any visit(s), the site staff should maintain regular telephone contact with the patient, or with a person pre-designated by the patient. This telephone contact should preferably be done according to the study visit schedule. Data will continue to be collected concerning the patients' condition and changes in concomitant medications, surgeries and procedures, serious and non-serious adverse events, and asthma exacerbations should be recorded in the appropriate eCRF if applicable. If necessary an unscheduled clinical visit may be arranged.

The investigator must also contact the IRT to register the patient's discontinuation from study treatment.

If study drug discontinuation occurs because treatment code has been broken, please refer to [Section 5.5.10](#)

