9.5.2 Safety variables

All safety data will be summarized for the SAF.

Safety summaries will be primarily based on on-treatment data with selected tables also presented for the all data after the first intake of study drug, while all data based safety data will be listed.

Secondary safety endpoints

The secondary endpoint of the rate of patients with at least one treatment emergent AE by primary system organ class will be presented descriptively and analyzed using a Cox regression model in a similar manner as the primary endpoint. A supportive analysis on the rate of patients with at least one AE by primary system organ class will be conducted similarly including all AEs starting on or after the time of the first intake of study drug (i.e., treatment emergent AEs and AEs occurring during the post-treatment follow-up).

The secondary endpoint of the rate of treatment emergent patient deaths and patient hospitalizations (any visit to the hospital requiring an overnight stay or an emergency room visit greater than 24 hours) due to an asthma exacerbation will be analyzed using a negative binomial regression model. The model will include randomization stratum (as in the analysis on primary endpoint), treatment group, severity of asthma (GINA steps 3, 4 and 5), and region as fixed class effects, with the natural logarithm of the duration of on-treatment follow-up in years as an offset variable. The duration of on-treatment follow-up in years will be calculated

for each patient as (treatment end date - treatment start date + 2 days)/365.25 without taking into account treatment interruptions. A supportive analysis of the rate of patient deaths and patient hospitalizations due to asthma exacerbations treatment emergent and after treatment discontinuation will be conducted similarly with the natural logarithm of the duration of follow-up in years as an offset variable.

In addition to the inferential analysis, summary statistics on the secondary safety variables will be presented as described below.

Adverse events

Adverse events after informed consent including asthma exacerbations will be summarized and listed. Summaries will include the number of patients with an event, exposure-adjusted incidence rates (patients with an event per patient year of follow-up to first event or censoring) and the percentage of patients with an event.

The following treatment emergent AE summaries will be produced:

- overall by system organ class and preferred term,

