2.8 Safety analyses

The primary and secondary objectives of the study are based on safety variables. All safety data will be summarized for the SAF.

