2.8.1 Adverse events (AEs)

Adverse events after informed consent including asthma exacerbations will be recorded. Adverse events that started during the study after informed consent and before the day of the first intake of study drug will be classified as prior adverse events and not included in tabulations of treatment emergent adverse events.

The following treatment emergent AE summaries will be produced by system organ class (SOC), preferred term (PT), treatment on overall population, by source of patients for:

1. all AEs,
2. all AEs by maximum severity,
3. suspected drug-related AEs,
4. AEs by standardized MedDRA query (SMQ) level
5. SAEs, and
6. AEs leading to permanent discontinuation of study-drug.

The number of patients experiencing an event, as well as the exposure-adjusted incidence rate (patients with events per 100 patient year of follow-up) will be provided in above summaries. Patient year of follow-up will be computed as (sum of the duration of exposure over patients, in days)/365.25. This method will account for the length of follow-up time under the assumption that events would occur with the same frequency at any point in time.

Summaries described above will also be produced by source of patients.

Post-treatment discontinuation AEs (events that start more than 7 days (30 days in the case of a serious AE) after the last intake of study drug) will be summarized separately in terms of number and percentage of patients with at least one AE.

Secondary endpoint: the rate of patients with at least one treatment emergent AE by primary system organ class

The number and proportion of patients with at least one treatment emergent AE by primary system organ class will be presented descriptively and analyzed using a logistic regression model stratified by randomization stratum (but not by region) and treatment group, severity of asthma (GINA treatment step 3, 4, and 5), and region as fixed class effects. Estimates of the odds ratios between QAW039 groups and placebo will be displayed along with associated 95% confidence intervals. Firth's penalized likelihood will be utilized for logistic regression for rare events.

Secondary endpoint: the rate of treatment emergent severe asthma exacerbation episodes requiring hospitalizations

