While no formal hypothesis testing is foreseen for the primary safety objectives, if both QAW039 doses have a 50% relative hazard increase for treatment emergent events, compared with placebo, then there will be approximately > 99%, 94% and 38% power that the two-sided 95% confidence interval not adjusted for multiplicity for one of the two QAW039 doses would exclude no effect for the primary safety variables of time-to-first treatment emergent AE, time-to-first treatment emergent SAE, and time-to-first treatment emergent AE leading to study treatment discontinuation analyzed across Treatment Period 1 and Treatment 2 combined, respectively. The power was estimated using 10,000 simulations based on 1,570 patients being randomized into the current study. In addition, the sensitivity of the power is further assessed for different scenarios of sample size (1470 patients and 1670 patients). This power will be higher, if more patients are randomized (e.g., due to additional new patients being enrolled) or more patients completing prior Phase 3 studies of QAW039 elect to participate in the current study.

The underlying assumptions for the power simulations were an exponential censoring rate in the placebo group of 0.22 and of 0.16 in the QAW039 treatment groups. The assumptions on the exponential event rate in each treatment group are shown in [Table 3-1](#). These assumptions are based on the, DREAM ([Pavord et al. 2012](#)) and MENSA ([Ortega et al. 2014](#)) trials, as well as a QAW039 Phase 2 study in moderate-to-severe asthma. The detailed power calculations are shown in the [Table 3-2 and Table 3-3](#).

Table 3-1 Assumed placebo event rates for power calculations

Endpoint	Previous study patients were enrolled in or new patients	Assumed exponential event rate (per patient-year)
Rate of AEs	QAW039A2316/ QAW039A2317	3.01

	QAW039A2307/ QAW039A2314	2.86
	New patients	2.86
Rate of SAEs	QAW039A2316/ QAW039A2317	0.07
	QAW039A2307/ QAW039A2314	0.24
	New patients	0.24
Rate of AEs leading to study treatment discontinuation	QAW039A2316/ QAW039A2317	0.03
	QAW039A2307/ QAW039A2314	0.03
	New patients	0.03

Table 3-2 Power (%) for a non-multiplicity adjusted confidence interval to exclude no-difference versus placebo for the primary safety variables

Primary Endpoint	Treatment Period	QAW039 150 mg versus placebo	QAW39 450 mg versus placebo	Both QAW039 150 mg and 450 mg versus placebo	One of the two QAW039 doses versus placebo
Time-to-first AE	1	>99	>99	>99	>99

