	1 & 2	>99	>99	>99	>99
Time-to-first SAE	1	65	65	54	76
	1 & 2	89	89	84	94
Time-to-first AE leading to study treatment discontinuation	1	16	16	9	22
	1 & 2	29	28	19	38

Power results are based on the sample size of 1570 randomized patients (1000 rollover patients plus 570 new patients).

Simulations were performed in SAS 9.4.

Table 3-3 power (%) for a non-multiplicity adjusted confidence interval to exclude no-difference versus placebo for the primary safety variables based on different sample size scenarios

Primary Endpoint	Treatment Period	QAW039 150 mg versus placebo	QAW39 450 mg versus placebo	Both QAW039 150 mg and 450 mg versus placebo	One of the two QAW039 doses versus placebo
Time-to-first AE	1	>99	>99	>99	>99
	1 & 2	>99	>99	>99	>99
Time-to-first SAE	1	62	62	50	73
	1 & 2	87	87	81	93
Time-to-first AE leading to study treatment discontinuation	1	14	14	8	21
	1 & 2	27	27	17	36
		30	30	20	40

Power results in the upper rows are based on the sample size of 1470 randomized patients (1000 rollover patients plus 470 new patients).

Power results in the lower rows are based on the sample size of 1670 randomized patients (1000 rollover patients plus 670 new patients).

Simulations were performed in SAS 9.4.

4 Change to protocol specified analyses

- In protocol, the secondary endpoints are stated in one sentence, i.e., the rate of treatment emergent patient deaths and patient hospitalizations (any visit to the hospital requiring an overnight stay or an emergency room visit greater than 24 hours) due to an asthma exacerbation. In the analysis plan, the endpoints are presented separately:
 - The rate of patient deaths due to a treatment emergent asthma exacerbation
 - The rate of treatment emergent severe asthma exacerbation episodes requiring hospitalizations
- In protocol, it is mentioned that the treatment emergent adverse events and prior adverse events are defined based on the time of the adverse event and intake of study drug. However since the time of start and end of adverse events are not captured for this study, the definition has been updated considering only the day of the adverse event and intake of study drug.
- The supportive analyses specified in protocol Section 9.4.4 will be performed for exposure incidence rate summaries rather than the primary outcome.

- Non-treatment emergent adverse events (AEs) in post-treatment follow-up period will be summarized separately.

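### SAP 2.8.1 reports post-treatment AEs and SAEs as a percentage of all treated patients, with no visible adjustment for how long each patient was observed after stopping drug

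*SAP*

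**What the plan says.** SAP 2.8.1 defines post-treatment events as "events that start more than 7 days (30 days in the case of a serious AE) after the last intake of study drug". These "will be summarized separately in terms of number and percentage of patients with at least one AE". The analysis set follows from SAP 2.8: "All safety data will be summarized for the SAF". The six treatment-emergent summaries in the same section also receive an exposure-adjusted rate, with patient-years taken from the duration of drug exposure.

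Follow-up after the last dose depends on how the patient stopped:

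- **Patients who complete treatment.** Protocol 5.6.1 places Visit 401 "30 days after last visit (299, Week 52 for patients not continuing into Treatment Period 2", or after Visit 399 for those completing Period 2. Table 6-1 has Visit 399 on Day 1092 and Visit 401 on Day 1120, which is 28 days.
- **Patients who stop drug early.** Protocol 5.6.2: "Patients who discontinue study treatment will be asked to remain in the study and complete all study visits". Serious and non-serious AEs continue to be collected from them.

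Protocol 9.5.2 attaches to its AE summaries "exposure-adjusted incidence rates (patients with an event per patient year of follow-up to first event or censoring" and plans AE and SAE summaries that combine treatment-emergent and post-treatment events. SAP section 4 declares the change in these words: "Non-treatment emergent adverse events (AEs) in post-treatment follow-up period will be summarized separately". It does not mention a rate for them.

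**The concern.** A percentage compares arms fairly when every patient in the denominator has about the same chance of being seen to have the event. Here they do not. A patient who takes drug to the last visit has no scheduled observation beyond day 30, so contributes nothing to the post-treatment SAE count, and has about three weeks in which a later non-serious AE can appear. A patient who stops early and stays can contribute months or years. Both count once in the safety set.

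The by-arm percentage therefore mixes the risk after stopping with the number and timing of early stops. The SAP adjusts for time on drug and makes no visible adjustment off drug, where observation is least even. At stake is the SAP's visible dedicated by-arm display of events that begin after these windows, which is where a delayed reaction would be looked for.

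**Working it through.** **Inputs.** SAP section 3 assumes an "exponential censoring rate in the placebo group of 0.22 and of 0.16 in the QAW039 treatment groups". Its placebo SAE rates are 0.24 per patient-year (A2307/A2314 rollovers and new patients) and 0.07 (A2316/A2317 rollovers). N is 1,570 at about 3:3:1, so about 224 placebo patients and 673 per dose. Maximum treatment is 156 weeks.

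**Step 1: reproduce a figure of the plan that uses these censoring rates.** The documents state no figure for post-treatment events. For time to first AE leading to discontinuation over both periods (rate 0.03, hazard ratio 1.5), the expected events are:

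- Placebo: 224.3 × 0.03/0.25 × (1 − e^(−0.75)) = 14.2
- Each dose: 672.9 × 0.045/0.205 × (1 − e^(−0.615)) = 67.8

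SE = √(1/14.2 + 1/67.8) = 0.292. Power = Φ(0.405/0.292 − 1.96) = 28.4%. The plan states 29% and 28%, so the rates are being read as the plan used them.

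**Step 2: who can be observed.** Treat the censoring rate d as the treatment discontinuation rate (assumption). The share stopping before 3 years is 1 − e^(−0.66) = 48.3% on placebo and 1 − e^(−0.48) = 38.1% on QAW039. The other 51.7% and 61.9% have no scheduled time for a post-treatment SAE.

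**Step 3: percentage shown at equal risk.** Let the SAE hazard h be the same in all arms after stopping, and let all discontinuers stay to horizon H. The 30-day lag and the 28-day follow-up nearly cancel. Ignoring the 2-day difference,

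P = (1 − e^(−dH)) − d(e^(−dH) − e^(−hH))/(h − d).

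For H = 3 and h = 0.24:

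- Placebo: 0.4831 − 0.22 × (0.5169 − 0.4868)/0.02 = 0.152
- QAW039: 0.3812 − 0.16 × (0.6188 − 0.4868)/0.08 = 0.117

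Keeping the 2 days, by numerical integration:

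| Horizon | h per year | Placebo | QAW039 | Ratio |
|---|---|---|---|---|
| 1 year | 0.24 | 2.2% | 1.7% | 0.74 |
| 2 years | 0.24 | 7.8% | 5.9% | 0.76 |
| 3 years | 0.24 | 15.2% | 11.7% | 0.77 |
| 1 year | 0.07 | 0.7% | 0.5% | 0.74 |
| 3 years | 0.07 | 5.2% | 4.0% | 0.77 |

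Observable time over 3 years is 0.80 years per placebo patient and 0.62 per QAW039 patient.

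**Step 4: vary the assumptions.**

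- *Partial retention.* Equal retention of 25% or 50% scales both arms and leaves the ratio essentially unchanged. Exit after stopping at 0.5 to 2 per year gives 0.74 to 0.78.
- *Shorter follow-up.* If patients who stop in Period 1 leave at Week 52, the figures at 0.24 are 8.5% vs 6.7% (ratio 0.79) when everyone still on drug enters Period 2, and 5.4% vs 4.2% (0.78) when half do.
- *Different QAW039 dropout.* At 0.19 or 0.25 per year the 3-year ratio is 0.89 or 1.10.
- *Non-serious AEs at 2.86 per year.* With about 23 days of observable time in completers: 53.2% vs 45.3% at 3 years (ratio 0.85) and 27.8% vs 24.9% at 1 year (0.90).

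**Step 5: what a different denominator does.** Over 3 years at 0.24, dividing by early discontinuers only gives 0.1516/0.4831 = 31.4% vs 0.1168/0.3812 = 30.6%. A rate per 100 patient-years of observed post-treatment time gives 24 vs 24.

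**The case against.** **The plan may contain more than is visible.** SAP section 4 moves the supportive analyses of protocol 9.4.4 to exposure-incidence summaries, and the content of 9.4.4 is not in the public text. A rate that includes post-treatment events cannot be ruled out, so a reader should not infer that the SAP has none. What stands is narrower: no adjustment is visible, and the patient-years defined in SAP 2.8.1 are time on drug, which is not the right denominator for events off drug.

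**Completers are not wholly unobservable.** Protocol 7.2.2 allows an SAE beyond 30 days to be reported when causality is suspected, whoever the patient is. It is tempting to say that a post-treatment SAE can be seen only in early discontinuers; that is true of scheduled collection only. The same section limits reports to the sponsor after day 30 to suspected cases, while 5.6.2 goes on recording serious AEs in the eCRF, so 0.24 per year may be too high. This lowers the percentages but barely moves the ratio.

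**The 3-year figures are a ceiling.** SAP 2.5.1 says the study was terminated early, Period 2 is optional, and full retention is unlikely. At 1 year the expected counts are about 5 placebo patients (224 × 2.25%) and 11 per dose (673 × 1.67%), too few to separate the artefact from chance.

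**The protocol did not plan a post-treatment-only rate.** Section 9.5.2 attached rates to AE summaries and planned combined tables. The SAP declares the split. It would be too strong to say that a promised post-treatment rate was withdrawn.

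**Consequences are limited.** The table is descriptive. Events soon after stopping fall inside the SAP's 7-day and 30-day treatment-emergent windows. The number discontinuing study medication is tabulated under SAP 2.4.1, so a careful reader could partly correct the percentage. All this lowers the priority without making the percentage comparable between arms.

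**Conclusion.** The point holds as a defect of one descriptive table. The post-treatment percentage depends on the amount and timing of early stopping in each arm as well as on risk. Under the plan's own censoring rates, read as discontinuation rates, with similar retention after stopping and equal risk, the SAE ratio would be about 0.74 to 0.79. The absolute gap runs from about half a percentage point (1 year) to 3.5 points (3 years, all retained) at 0.24 per year, and is about a third of that at 0.07.

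Two stronger readings are not supported. One is that QAW039 will look safer than it is: actual dropout by arm is unknown, and higher dropout on QAW039 would reverse the artefact. The other is that a real excess will be hidden: under the 3-year, 0.24 assumptions a true hazard ratio of 1.42 would appear as no difference, but that is an illustration under assumed rates, and the counts are still shown. The primary and secondary endpoints are treatment-emergent and unaffected. This is a cheap improvement of minor to moderate priority.

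**What to change.** In SAP 2.8.1, for post-treatment AEs and SAEs by arm:

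1. Add patients with an event per 100 patient-years of post-treatment observation. Start the clock at last dose + 8 days (+ 31 days for SAEs) and stop it at the first such event or the date of last contact.
2. Base the percentage on patients with any such observation time, and show the number at risk and the patient-years in each column.
3. Add a footnote that the comparison covers patients who stopped drug and remained under observation and is not a randomized comparison. State that causality-suspected late reports from patients without scheduled observation are listed separately.

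The cost is a few lines of SAP text and one derived variable. Date of last contact is already defined in SAP 2.1.1.5, and last dose date is already used in SAP 2.4.1. No new data or change in conduct is needed. The rate will rest on few events if follow-up was short, and patients who stop and stay are a selected group, so it should be read as description.

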2.5 Analysis of the primary objective

2.5.1 Primary endpoint

Primary endpoints for the study are:

Treatment Period 1:

- Time-to-first treatment emergent adverse events (AEs);
- Time-to-first treatment emergent serious adverse events (SAEs); and
- Time-to-first treatment emergent AE leading to discontinuation from study treatment.

of QAW039 (150 mg once daily and 450 mg once daily), compared with placebo in patients with moderate-to-severe asthma receiving SoC asthma therapy.

Treatment Period 1 and Treatment Period 2 combined:

- Time-to-first treatment emergent adverse events (AEs);
- Time-to-first treatment emergent serious adverse events (SAEs); and
- Time-to-first treatment emergent AE leading to discontinuation from study treatment.

of QAW039 (150 mg once daily and 450 mg once daily), compared with placebo in patients with moderate-to-severe asthma receiving SoC asthma therapy.

As this study has been early terminated, the primary endpoint will be analyzed in the way of combined treatment period 1 and treatment period 2. Treatment emergent AEs are defined as adverse events (including asthma exacerbations), starting on or after the day of the first intake of study drug in this study and until the earlier date out of: date of last intake of study drug +7 days (30 days in the case of a serious AE) and final visit.

Any AEs that started during the study after informed consent and before the time of the first intake of study drug will be classified as a prior AE and not classified as treatment emergent AE. The time-to-first treatment emergent AE is defined as the time to the occurrence of an AE from the treatment start date, and computed as time to AE=AE start date – treatment start date +1 day. As a general rule of censoring, patients who either completed the study or discontinued

treatment prematurely or continued treatment and without the event of interest will be censored at the minimum out of the dates of last medication intake + 30 days, final visit date, and date of death. Time-to-first treatment emergent SAEs and time-to-first treatment emergent AEs leading to discontinuation from study treatment are defined in a similar manner as time-to-first treatment emergent AE.

The definition and rationale for the estimand for the primary endpoint are given in [Table 2-1](#). The statistical strategy to handle each intercurrent event is described in more detail in [Section 2.5.3](#).

Table 2-1 Summary of estimand for the primary endpoint

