- AEs of special interest are only presented descriptively. Time-to-first-event analyses using Kaplan-Meier plots and Cox regressions as well as incidence for recurrent events per patient year will not be presented.
- The secondary endpoint of the rate of patients with at least one treatment emergent AE by primary system organ class will be analyzed using a logistic regression model instead of a Cox regression model.
- Shift tables relative to the normal reference ranges to summarize the on-treatment change from baseline to post-baseline for each laboratory parameter or ECG parameter or vital sign assessments will not be presented.

█ [REDACTED]

[figure not shown]
- In protocol, treatment emergent adverse events (TEAEs) were defined as AEs starting on or after the time of the first intake of study drug and until the day after the last intake of study drug. This definition was updated in analysis based on clinical and safety consideration as follows: adverse events (including asthma exacerbations), starting on or after the day of the first intake of study drug in this study and until the dates of last intake of study drug +7 days (30 days in the case of a serious AE) .

█ [REDACTED]

█ [REDACTED]

- Subgroup analyses on primary outcomes are removed.

[REDACTED]

6 Appendix

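### SAP 2.8.1 replaces the protocol's Cox model for first AE by system organ class with a logistic model without follow-up time, so its odds ratio shifts if dropout differs by arm; restoring Cox is a cheap improvement.

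*SAP*

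**What the plan says.** Protocol 9.5.2 states that the rate of patients with at least one treatment emergent AE by primary SOC "will be presented descriptively and analyzed using a Cox regression model in a similar manner as the primary endpoint". SAP 2.8.1 states that the same endpoint will be "analyzed using a logistic regression model stratified by randomization stratum (but not by region", with treatment group, GINA step and region as class effects. It reports odds ratios against placebo with 95% intervals and uses Firth's penalized likelihood for rare events. The model has no follow-up term or offset. SAP section 4 declares the switch: the endpoint "will be analyzed using a logistic regression model instead of a Cox regression model". That bullet gives no reason.

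Three other places bear on the point.

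- **Event window.** SAP 2.5.1 counts an event as treatment emergent up to the earlier of the final visit and "date of last intake of study drug +7 days (30 days in the case of a serious AE"). Its general rule for patients without an event is that they "will be censored at the minimum out of the dates of last medication intake + 30 days", final visit or death.
- **Dropout.** Protocol 9.8 and SAP section 3 base the power simulations on "an exponential censoring rate in the placebo group of 0.22 and of 0.16 in the QAW039 treatment groups".
- **Exposure-adjusted rates.** Protocol 9.5.2 defines them as "exposure-adjusted incidence rates (patients with an event per patient year of follow-up to first event or censoring"). SAP 2.8.1 keeps such rates by SOC but changes the denominator: "Patient year of follow-up will be computed as (sum of the duration of exposure over patients, in days)/365.25".

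**The concern.** A patient who stays on treatment longer has more time to record a first event that counts. A model of whether an event ever occurred treats six months and two years at risk alike. If the arms differ in time on treatment, the odds ratio mixes the drug effect with that difference. Discarding event times can also lose information in SOCs where many patients have an event.

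Period 2 is optional and the SAP says the study was terminated early, so follow-up certainly varies between patients. Variation alone does not bias the comparison; a difference between arms does. At stake is the model-based SOC comparison with placebo in a trial whose purpose is long-term safety.

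**Working it through.** **Inputs from the documents.** N = 1,570 at 3:3:1, so 1,570 × 3/7 ≈ 673 per dose and 1,570/7 ≈ 224 placebo. Hazard ratio 1.5. Two-sided 95% intervals, unadjusted. Dropout 0.22 (placebo) and 0.16 (QAW039) per year.

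**Assumptions, because the documents give no figure.** Placebo SOC rates λ of 0.05, 0.3, 0.6 and 1.0 per patient-year; planned follow-up T uniform on 0.25-2 years.

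**Check against the plan's own power.** For AEs leading to discontinuation (0.03 per year), expected events per arm are n·[λ/(λ+c)]·(1 − exp(−(λ+c)T)), where c is the dropout rate.

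- T = 1: 5.95 placebo and 27.38 active events. z = ln 1.5 / √(1/5.95 + 1/27.38) = 0.896, so power = Φ(0.896 − 1.96) = 14.4%.
- T = 3: 14.18 and 67.86 events, z = 1.389, power 28.4%.

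The plan states 16% and 28-29%. A simulated Cox model gives 16.6-16.8% and 31-32%. The inputs therefore reproduce the plan's figures closely. The plan gives no power for the SOC endpoint.

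**Null odds ratio in closed form.** With treatment ending at the earlier of dropout and T, and events counted to +7 days:

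P = 1 − exp(−7λ/365.25) × mean over T of [c/(c+λ)·(1 − exp(−(c+λ)T)) + exp(−(c+λ)T)].

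Example at λ = 1.0 with no drug effect: P = 0.5783 on placebo (c = 0.22) and 0.5939 on QAW039 (c = 0.16). OR = (0.5939/0.4061)/(0.5783/0.4217) = 1.066.

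| SOC rate per PY | 0.05 | 0.3 | 0.6 | 1.0 |
|---|---|---|---|---|
| Null OR, dropout 0.22/0.16 | 1.039 | 1.046 | 1.055 | 1.066 |
| Null OR, equal dropout 0.19/0.19 | 1.000 | 1.000 | 1.000 | 1.000 |
| Null OR, reversed 0.16/0.22 (hypothetical) | 0.962 | 0.956 | 0.948 | 0.938 |

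**Both models on the same simulated trials** (224 vs 673; unadjusted, Wald intervals; 12,000 null trials and 10,000 trials at HR 1.5 per cell):

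| SOC rate per PY | 0.05 | 0.3 | 0.6 | 1.0 |
|---|---|---|---|---|
| Null, 0.22/0.16: CI excludes 1, logistic (%) | 4.5 | 5.7 | 6.1 | 7.2 |
| same, Cox (%) | 4.6 | 5.2 | 4.8 | 4.9 |
| HR 1.5, 0.22/0.16: CI above 1, logistic (%) | 22.8 | 84.0 | 95.0 | 96.8 |
| same, Cox (%) | 19.2 | 79.6 | 95.1 | 98.5 |
| HR 1.5, 0.19/0.19: CI above 1, logistic (%) | 19.1 | 76.7 | 89.6 | 92.5 |
| same, Cox (%) | 19.0 | 80.6 | 95.4 | 98.6 |

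With equal dropout the logistic loss is 80.6 − 76.7 = 3.9, 95.4 − 89.6 = 5.8 and 98.6 − 92.5 = 6.1 points in the three commoner SOCs, and nothing in the rare one. Under the plan's dropout the upward shift offsets this: the logistic model gains 4.4 points at 0.3, is level at 0.6 and loses 1.7 at 1.0.

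**Sensitivity to follow-up.** With one fixed year, the null OR at 0.22/0.16 is 1.03-1.06 and the equal-dropout power loss is 0-2 points. With follow-up uniform on 0.1-3 years, that loss is about 7-14 points for rates of 0.24-1.0.

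**Exposure-adjusted rates on total exposure.** The null ratio is 0.99-1.01, so the shift is largely removed. But a true HR of 1.5 with equal dropout appears as 1.48, 1.38, 1.29 and 1.21 at the four rates, because time after the first event stays in the denominator. On follow-up to first event or censoring, expected events equal λ times that follow-up under a constant hazard, so the ratio returns to 1.5.

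**Censoring at +30 rather than +7 days** for patients without an event moves the Cox hazard ratio by at most 0.006.

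**The case against.** The change is declared. The endpoint is worded as patients with at least one event, which a proportion model answers directly, and Firth's penalty is sensible for sparse SOCs. No formal testing is planned even for the primary objectives, so power is a soft yardstick. All of this stands, and it limits the weight of the point. It does not restore follow-up time to the comparison.

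The simulation also favours Cox: it has constant hazards and dropout unrelated to events, and it omits strata, covariates and Firth. Few SOCs can be common. The overall first-AE rate is 2.86-3.01 per patient-year, and if SOC events were independent their rates would sum to that total; 0.3 + 0.6 + 1.0 = 1.9 already uses about two-thirds. Both limits stand.

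A reader might infer more than the documents support:

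- *The logistic model hides harm.* That needs higher dropout on QAW039 than on placebo. The plan's inputs run the other way, and realised dropout is not given.
- *It loses power in general.* The loss appears with equal dropout, not under the plan's inputs.
- *The distortion is large.* Full three-year follow-up would give null odds ratios of 1.09-1.28, but the SAP says the study ended early.
- *No other inferential SOC comparison exists.* SAP section 4 applies the supportive analyses of protocol 9.4.4 to the exposure incidence rate summaries. Section 9.4.4 is not visible, so this is only the sole visible model-based SOC comparison.

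**Conclusion.** The concern holds in a limited form. SAP 2.8.1 drops follow-up time from a comparison for which the protocol had included it, and states no reason. Under the plan's dropout inputs, the odds ratio without a drug effect is 1.04-1.07, and false exclusion of 1 rises to about 7% in the commonest SOCs, with no inflation in rare ones. The error is toward flagging harm and costs no material power. If dropout is equal there is no shift, but about 4-6 points of power are lost at rates of 0.3-1.0 per patient-year; the loss is smaller with shorter follow-up and larger with longer. Separately, the changed exposure denominator shrinks a true effect in common SOCs.

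The sizes rest on assumed SOC rates, an assumed follow-up distribution and simplified models. The direction of any shift depends on which arm stays on treatment longer, and a safety comparison should not depend on that. The three primary endpoints keep Cox models, so this is an inexpensive improvement to a secondary analysis and does not threaten the main results.

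**What to change.** In SAP 2.8.1:

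1. Make the protocol's Cox model the inferential analysis: time to first treatment emergent AE within each SOC, with the terms and model-reduction steps of SAP 2.5.2 and a Firth penalty for sparse SOCs. Report hazard ratios against placebo with 95% intervals.
2. Censor patients without an event at the end of the treatment emergent window rather than at +30 days for everyone. This is a minor point numerically. Because the window is 7 days for non-serious and 30 days for serious events, state how a first serious event on days 8-30 enters the risk set.
3. Keep the logistic odds ratios as supportive.
4. Compute the exposure-adjusted rates on follow-up to first event or censoring, as in protocol 9.5.2.
5. Amend the SAP section 4 bullet to match.

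No new data are needed, and the primary-analysis code can be reused per SOC. The cost is a little more programming and fewer covariates in sparse SOCs.
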